2.2.2 Trial schema

A summary of the trial as a flow diagram is displayed in [Figure 1](#). For the planned assessments and visits, see the Schedule of Activities (SoA) in Section 1.3 of the trial protocol (version 7.0; 28Jun2023).

Figure 1. Schema – Safety and immunogenicity of SARS-CoV-2 monovalent and multivalent RNA-based vaccines in healthy subjects

* An optional additional lower dose level may be tested in each of the Cohorts in up to 20 additional subjects per Cohort.

** No history of COVID-19 and/or clinical or evidence of prior infection with SARS-CoV-2 at screening (Visit 0).

Abbreviations: "A" = assignment to Cohort; "R" = randomization.

3 ENDPOINTS AND BASELINE VARIABLES: DEFINITIONS AND CONVENTIONS

3.1 Primary endpoints

The primary objective for Part A is solely based on safety endpoints, however Part B and Part C also have immunogenicity endpoints that are also primary objectives.

3.1.1 Safety endpoints for Parts A, B, and C

For subjects in each cohort, in Part A, Part B and Part C of this trial, who received at least 1 dose of trial IMP (Investigational Medicinal Product), the primary safety endpoints are:

- Local reactions up to 7 days after each dose.
- Systemic events up to 7 days after each dose.
- Adverse events (AEs) from:
 - Dose 1 up to 1 month after Dose 1
 - Dose 2 up to 1 month after Dose 2
 - Dose 3 up to 1 month after Dose 3
- Serious adverse events (SAEs) from Dose 1 up to 6 months after the last dose.

For Cohorts 1, 3, 4, 5, 7, and 8, last dose is Dose 1. Dose 2 is the last dose for subjects in Cohort 2 and Dose 3 is the last dose for subjects in Cohort 6. Cohort 9 participants are not dosed therefore their safety data will not contribute to the primary safety endpoint.

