## Part B

Part B will be initiated after review of reactogenicity and available immunogenicity data of Part A (Cohorts 1, 4, 6) by the SRC.

Part B consists of three cohorts of n = 300 subjects each (~375 subjects will be enrolled in each cohort to ensure there are 300 evaluable subjects), which will enroll subjects 18 to 85 years old; ~60% of these subjects should be 18 to 55 years old and ~40% should be 56 to 85 years old:

- **Cohort 1** will enroll subjects from the trial BNT162-02 / C4591001 who received two injections of 30 µg BNT162b2, at least 6 months after the second BNT162b2 dose. Subjects will receive on Day 1 one dose of 30 µg multivalent vaccine BNT162b2 (B.1.1.7 + B.1.617.2).
- **Cohort 4** will enroll subjects from the trial BNT162-02 / C4591001 who received two injections of 30 µg BNT162b2, at least 6 months after the second BNT162b2 dose. Subjects will receive on Day 1 one dose of 30 µg monovalent vaccine BNT162b2 (B.1.617.2).
- **Cohort 6** will enroll subjects who have not received any prior prophylactic vaccine against COVID-19. Subjects will receive 30 µg multivalent vaccine BNT162b2 (B.1.1.7 + B.1.617.2), one each on Day 1 and Day 21 and the third dose ~6 months after the second dose. Approximately 15 subjects at preselected sites in Part B will be evaluated in terms of cell-mediated immunity.

Part B will expand the safety information of the multivalent vaccine BNT162b2 (B.1.1.7 + B.1.617.2) as one booster dose in BNT162b2-experienced subjects, and as two-dose, primary vaccination regimen in subjects who are COVID-19 vaccine-naïve and have not experienced COVID-19.

Part B will also determine based on geometric mean ratios (GMR) of neutralizing titers and seroresponse rate, if the immune response of the multivalent vaccine BNT162b2 (B.1.1.7 + B.1.617.2) against the B.1.1.7 and the B.1.617.2 strains or immune response after one

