3.1.1.3 Adverse events and serious adverse events

For all dosed trial subjects in cohorts 1-8, AEs will be collected from each dose up to 1 month after this dose and for subjects in cohort 9 - from the Visit 1 (after eligibility is confirmed) up to 1 month. However, for any visit more than 1 month after each IMP injection (cohorts 1-8) or Visit 1 (cohort 9), only IMP-related AEs, trial procedure-related AEs, adverse events of special interest (AESIs), SAEs, and AEs linked to confirmed COVID-19 cases will be recorded.

Solicited AEs (i.e., reactogenicity events) that are derived from trial subjects' e-diaries should not be reported as AEs unless the event meets criteria for an SAE or starts after Day 7 or starts on Days 1 to 7 and continues past Day 7.

In addition, all solicited Grade 4 reactogenicity events should be medically confirmed.

An AE/SAE is defined as treatment-emergent adverse event (TEAE) if the event onset date and time is after the first IMP dose (if the event was absent before the first administration of the IMP) or worsened after the first IMP dose (if the event was present before the first administration of the IMP).

In the event of an incomplete onset date, the event will be considered as treatment-emergent unless the partial onset date information or complete or partial end date confirms the onset date or the event end prior to the first dose of IMP.

Missing AE date will be addressed as described in [Section 5.3](#).

All AEs and SAEs will be coded/categorized according to terms in Medical Dictionary for Regulatory Activities (MedDRA®) version 26.0 or higher.

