3.4.2 Trial day and analysis visits

Trial day:

Trial day will be calculated in reference to Day 1, defined as the date of first dose of trial IMP administration. For assessments conducted after Day 1, trial day is calculated as (assessment date – Day 1 date +1). For assessments conducted before Day 1, trial day is calculated as (assessment date – Day 1 date). There will be no Trial Day 0.

Analysis visits:

For clinical safety data summary, lab data, vital signs, electrocardiogram (ECG), and physical exam, the analysis visits post vaccination will be based on the visits reported and validated in the EDC database.

For immunogenicity assays, the sampling windows with grace period specified in [Table 7](#) will be used to define the valid samples to include in the Immunogenicity Analysis Set, and the per protocol sampling windows will be used to define the valid samples to include in the Immunogenicity Analysis Per Protocol Set. See [Table 8](#) for the definitions of the analysis sets.

Table 7. Immunogenicity sampling windows

Visit relative to dose	Window per CTP = Include in (per protocol) Immunogenicity Analysis Set	Additional grace period = No impact on immunogenicity = Include in Immunogenicity Analysis Set	Impact on immunogenicity = Exclude from Immunogenicity Analysis Set Important PD if supporting a primary endpoint. Non-important PD if not supporting a primary endpoint
1 week post dose	8+2 8-10 days	NAP	All OOW
3 weeks post dose	21±3 18-24 days	+/- 2 x days OOW ≥16 to ≤26 days	+/- 3 days and more OOW <16 days or >26 days
1 month post dose	29±3 26-32 days	+/- 7 days OOW ≥19 to ≤39 days	+/- 8 and more days OOW <19 days or >39 days
3 months post dose	85±5 80-90 days	+/- 7 x days OOW ≥73 to ≤97 days	+/- 8 and more days OOW <73 days or >97 days
6 months post dose	180±10 170-190 days	+/- 7 x days OOW ≥163 to ≤197 days	+/- 8 and more days OOW <163 days or >197 days
1 year post dose	360±10 350-370 days	+/- 14 x days OOW ≥336 to ≤384 days	+/- 15 and more days OOW <336 days or >384 days

Grace period will not be applied.

Abbreviations: OOW = out of window; NAP = not applicable; PD = protocol deviation.

The following conversion rules will be used to convert days to months and days to years:

- 1 month = 30.4375 days
- 1 year = 365.25 days

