6.1.1.1 Safety overview

The number of events, number and percentage of subjects reporting at least one of the below events from IMP administration will be summarized by treatment group post each dose and combined total of events for the periods from each dose up to 1 month after each dose based on Safety Set.

- Solicited local reactions and systemic events
- Any TEAE
- Related TEAE
- TEAE with Grade ≥ 3
- Related TEAE with Grade ≥ 3
- Any solicited AE that starts on Days 1 to 7 and continues longer than 7 d post-vaccination or starts after Day 7 or is an SAE
- Any SAE
- Related SAE
- SAE with Grade ≥ 3
- Related SAE with Grade ≥ 3
- TEAE leading to trial withdrawal
- TEAE leading to treatment withdrawal
- Any AESI
- All cause death

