6.1.1.4 Adverse events

The number of events, number and percentage of subjects reporting a treatment-emergent adverse event (TEAE) up to 1 month post each dose will be summarized by system organ class (SOC) and preferred term (PT) in descending order of frequency within both SOC and PT. Where a subject has the same TEAE, based on SOC or PT, reported multiple times in the same category the subject will only be counted once at that system organ class/preferred term.

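### In Cohort 6 the Dose 1 adverse-event period runs about 8 to 10 days past Dose 2, so some AEs belong to both by-dose summaries.

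*SAP*

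**What the plan says.** SAP Section 3.1.1 lists the primary AE endpoint as separate periods, including "Dose 1 up to 1 month after Dose 1" and "Dose 2 up to 1 month after Dose 2", with a third for Dose 3. Section 3.1.1.3 repeats the rule for collection: "AEs will be collected from each dose up to 1 month after this dose".

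The safety overview in SAP 6.1.1.1 tabulates events after each dose and adds a "combined total of events for the periods from each dose up to 1 month after each dose based on Safety Set". SAP 6.1.1.4 summarizes treatment-emergent AEs by SOC and PT over the same one-month period after each dose.

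In Protocol Section 4.1 (Part B), Cohort 6 subjects receive the multivalent vaccine "one each on Day 1 and Day 21 and the third dose ~6 months after the second dose"; Part A Cohort 6 has the same schedule. Protocol Tables 3 and 5 give the Dose 2 visit as 21±3. The SAP's conversion rule in Section 3.4.2 is "1 month = 30.4375 days".

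**The concern.** The one-month period suits Cohort 2, where Dose 2 is on Day 56 and the schedule has a one-month visit after Dose 1. It does not suit Cohort 6. In the Part A schedule (Protocol Table 3), Day 29 is already the one-week visit after the second vaccination, and there is no one-month visit after the first. One month after Dose 1 therefore falls about a week after Dose 2 by the protocol's own calendar.

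An AE starting on Day 23, two days after a Day 21 Dose 2, meets both the Dose 1 and the Dose 2 rule. The overview covers related TEAEs, Grade ≥3 TEAEs, SAEs and AESIs. Read literally, an anaphylaxis minutes after Dose 2 would also appear in the post-Dose 1 column. The Dose 1 profile in vaccine-naïve subjects would then include reactions to Dose 2, and any contrast between the doses would be blurred.

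**Working it through.** **Inputs**
- Dose 1 on Day 1; Dose 2 on Day 21, window Day 18 to 24 (Protocol Tables 3 and 5).
- Length of a month: either the one-month visit at Day 29 (28 days after a Day 1 dose; Protocol visit schedules and SAP Table 7) or 30.4375 days (SAP 3.4.2). Table 7 governs immunogenicity samples, so Day 29 is used here only as an alternative reading.

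**Check against the plan's own calendar.** The documents state no overlap figure, but they do place later one-month visits.
- Part A Cohort 6: 21 + 30.4375 = 51.4; the schedule says Day 51.
- Part A Cohort 2: 56 + 30.4375 = 86.4; the schedule says Day 86.

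The 30.4375-day reading fits these visits. Table 5 (Part B Cohort 6) instead uses 29±3 relative to the last dose, so both readings are kept.

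**Overlap = end of the Dose 1 period − day of Dose 2.** The period ends at Day 29 or at Day 1 + 30.4375 = Day 31.4.

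| Dose 2 on | Month ends Day 29 | Month = 30.4375 days |
|---|---|---|
| Day 18 | 29 − 18 = 11 days | 31.4 − 18 = 13.4 days |
| Day 21 | 29 − 21 = 8 days | 31.4 − 21 = 10.4 days |
| Day 24 | 29 − 24 = 5 days | 31.4 − 24 = 7.4 days |

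**Share of the Dose 1 period.** At Day 21: 8/28 = 29% or 10.4/30.4 = 34%. The extremes are 5/28 = 18% and 13.4/30.4 = 44%.

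**Where there is no overlap**
- Cohort 2: the earliest Dose 2 is Day 53, and 53 − 31.4 = 21.6 days after the Dose 1 period ends.
- Planned Dose 3 in Cohort 6: the Dose 2 period ends by 24 + 30.4 = Day 54.4, and Dose 3 is planned about 6 months after Dose 2.
- A Cohort 6 subject with no Dose 2, or with Dose 2 after about Day 31.

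**Could another rule remove the overlap?**
- SAP 3.1.1.3 defines treatment emergence against the first IMP dose only.
- SAP 6.1.1 restricts percentages after Doses 2 and 3 to subjects who received those doses. That does not keep post-Dose 2 events out of the Dose 1 numerator.
- SAP 6.1.1.4 counts a subject once per SOC or PT within a summary, not across dose periods.
- SAP 3.1.1.1 and 3.1.1.2 calculate onset from each dose date, but only for e-diary reactions.

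None of these ends a period at the next dose or assigns an AE to the latest dose.

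**Ceiling on subjects.** Planned enrollment in Cohort 6 is 375 (Part B) + 20 (Part A) = 395.

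**The case against.** The strongest reply is that most of what happens in the days just after a vaccination is solicited reactogenicity, and the plan keeps that out of the AE data. Under SAP 3.1.1.3 and Protocol 8.3, e-diary events become AEs only if they are serious, start after Day 7, or persist past Day 7. The overview does list solicited reactions as a row, but SAP Sections 3.1.1.1, 3.1.1.2 and 5 tie them to the seven days after each injection. This stands, and it narrows the point to unsolicited AEs and the excepted solicited events.

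It can also be said that double counting is inferred. The programming specifications are not available, later visits are labeled as follow-up to the second vaccination, and a combined total over periods may mean the union of those periods. For the combined total this stands. For the by-dose columns it does not: visit labels are not an AE rule, and the written periods overlap.

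The protocol's AE estimand can be read cumulatively and does not itself demand exclusive attribution by dose. However, SAP 3.1.1 splits it into separate dose periods, and the tables follow that split.

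Two stronger readings are tempting.
- **A fixed inflation figure.** A reader might divide 8 days by the roughly 20 days before Dose 2 and conclude that Dose 1 counts rise by 8/20 = 40%. That needs a constant daily AE rate, which the documents do not give. It also applies to event counts, whereas the estimand is a percentage of subjects; a subject who already has an AE before Dose 2 adds nothing to that percentage.
- **Damage to a single-dose safety claim.** The one-dose objective in Protocol version 7.0 concerns immunogenicity only. The Cohort 6 safety objective covers three doses, and no single-dose safety objective is set.

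Finally, no hypothesis depends on these tables, and planned subject listings should let a reader recover onset relative to each dose. Both are true. They limit the consequence but do not correct the summaries.

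**Conclusion.** The point holds in this limited form. As written, the Cohort 6 Dose 1 AE period includes about 8 to 10.4 days after a Dose 2 given on Day 21 (5 to 13.4 days across the Dose 2 window). Qualifying AEs with onset in that time meet both definitions. The range rests on the Day 18 to 24 Dose 2 window and the two readings of one month.

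The consequence is confined to descriptive by-dose AE summaries. The primary SAE endpoint, which runs from Dose 1 to 6 months after the last dose, is not split by dose and is unaffected; the SAE rows in the by-dose overview are affected. How far the AE percentages move cannot be determined without AE rates over time. The 395 subjects are a ceiling, because a missed or sufficiently delayed Dose 2 (delays are allowed for in Protocol 7.1.2) removes the overlap. The correction is worth making because it is cheap.

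**What to change.** In SAP 3.1.1, 6.1.1.1 and 6.1.1.4:
- For by-dose AE summaries, close each period at one month after that dose or at the next IMP dose, whichever comes first, so that each AE goes to the most recent dose before its onset.
- State that the combined total counts each event once.
- Note that the Cohort 6 Dose 1 period is then about 20 days (17 to 23 across the Dose 2 window) against about 30 for Dose 2. Report period length or exposure-adjusted rates wherever doses are compared.
- Record the change in SAP Section 8, since it shortens the one-month period for these summaries. SAP 8.3 says the protocol can no longer be amended, so the SAP and the clinical study report are the places for it.

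The cost is a few sentences and a date-time condition in the AE derivation. Injection date and time (Protocol 6.4) and AE onset date and time (Protocol 10.3.1.7) are already recorded, so no new data are needed and no test changes. The real cost is the unequal period length, which the third item addresses.

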3.1.1.1 Local reactions

The local reactions assessed by trial subjects and reported in the e-diary are pain at the injection site, tenderness, erythema/redness, induration/swelling, from Day 1 through Day 7 after each trial IMP dose, where Day 1 is the day of each IMP injection. A subject is deemed to have had a local reaction if they report the reaction as “yes” on any day of the e-diary recording period (i.e., Day 1 through Day 7 inclusive).

For redness and swelling, the reported size must be at least 2.5 cm (0.98 inches) to be deemed as a local reaction. Redness and swelling with a size less than 2.5 cm will not be included in the analysis.

Solicited local reactions will be categorized as mild, moderate, severe, or potentially life-threatening) and graded from 1 to 4, during the analysis as described in Table 5. The categories and grades are based on the FDA Guidance for Industry: [“Toxicity Grading Scale for Healthy Adult and Adolescent Volunteers Enrolled in Preventive Vaccine Clinical Trials”](#).

Table 5. Local reaction grading scale

	Mild (Grade 1)	Moderate (Grade 2)	Severe (Grade 3)	Potentially life-threatening (Grade 4)
Pain at the injection site	Does not interfere with activity	Interferes with activity	Prevents daily activity	Emergency room visit or hospitalization for severe pain
Tenderness	Mild discomfort to touch	Discomfort with movement	Significant discomfort at rest	Emergency room visit or hospitalization
Erythema /redness ^a	2.5 cm to 5.0 cm (0.98 in to 1.96 in)	>5.0 cm to 10.0 cm (>1.96 in to 3.94 in)	>10 cm (>3.94 in)	Necrosis or exfoliative dermatitis
Induration /swelling ^b	2.5 cm to 5.0 cm (0.98 in to 1.96 in)	>5.0 cm to 10.0 cm (>1.96 in to 3.94 in)	>10 cm (>3.94 in)	Necrosis

- a) In addition to grading the measured local reaction at the greatest single diameter, the measurement should be recorded as a continuous variable.
- b) Induration/swelling should be evaluated and graded using the functional scale as well as the actual measurement.

For subjects recording at least one local reaction from Day 1 through Day 7 after IMP injection:

- The maximum severity grade is equal to the highest graded local reaction within the recording period.
- Duration will be calculated in days as the difference from the start of the first reported event to the resolution of the last reported event, inclusive. The resolution date for events lasting longer than 7 days was recorded in the subject's adverse event case report form. If the resolution date is partial or missing, the duration will be considered unknown.
- Onset day, defined as the first day of reporting any severity, will be derived for each recorded local reaction. If a subject report changes in severity of the local reaction, only the first day of reporting that specific local reaction will be counted. Local reaction onset day for Dose 1 will be calculated from the IMP Dose 1 injection date, for Dose 2 from the IMP Dose 2 date and for Dose 3 from the IMP Dose 3 date.

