### 8.2.3 **Subject e-diaries for assessment of reactogenicity (local and systemic reactions)**

Subject e-diaries will be issued, trained, and collected by trial site personnel at the visits given in the SoA (Section 1.3).

The trial site personnel will remind the subject to record the worst grade for each symptom in the e-diary at approximately the same time every evening on the day of IMP injection and then every day in the evening for a total of seven consecutive days.

The trial site personnel will remind the subject to measure their oral body temperature using the provided thermometer or device and record their oral body temperature in the e-diary every day including the day of IMP injection.

The reporting on the CRF of local and systemic reactions will be based on the subject's assessments only.

The trial site personnel should review daily the e-diary entries of their trial subjects.

All reported Grade 4 local and/or systemic reactions must be confirmed by an investigator or a medically qualified person.

The grading of reported solicited local and systemic reactions will be performed using the grading scale tables given in Sections 8.2.3.1 and 8.2.3.2, which are based on the FDA Guidance for Industry "[Toxicity Grading Scale for Healthy Adult and Adolescent Volunteers Enrolled in Preventive Vaccine Clinical Trials](#)".

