**Table 9: Local reaction grading scale**

	Mild (Grade 1)	Moderate (Grade 2)	Severe (Grade 3)	Potentially life-threatening (Grade 4)
Pain at the injection site	Does not interfere with activity	Interferes with activity	Prevents daily activity	Emergency room visit or hospitalization for severe pain
Tenderness	Mild discomfort to touch	Discomfort with movement	Significant discomfort at rest	Emergency room visit or hospitalization
Erythema/rednessa	2.5 cm to 5.0 cm (0.98 in to 1.96 in)	>5.0 cm to 10.0 cm (>1.96 in to 3.94 in)	>10 cm (>3.94 in)	Necrosis or exfoliative dermatitis
Induration/swellingb	2.5 cm to 5.0 cm (0.98 in to 1.96 in)	>5.0 cm to 10.0 cm (>1.96 in to 3.94 in)	>10 cm (>3.94 in)	Necrosis

a. In addition to grading the measured local reaction at the greatest single diameter, the measurement should be recorded as a continuous variable.

b. Induration/swelling should be evaluated and graded using the functional scale as well as the actual measurement.

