#### Reactogenicity

Solicited local and systemic reactions (from the subject e-diary) will be summarized using the Safety Set. In general, solicited reactions will be analyzed for each immunization, i.e.:

- Up to 7 d after each IMP injection

For each injection, the number and percentage of subjects reporting at least one local reaction or systemic reaction (i.e., solicited data collected using subject e-diaries) will be summarized for each of the following types using the Safety Set:

- Any local reactions or systemic reactions
- Grade  $\geq 3$  local reactions or systemic reactions

Moreover, the number and percentage of subjects reporting at least one local reaction will be summarized by worst grade using the Safety Set.

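### The SAP's 2.5 cm floor for redness and swelling has no exception for Grade 4, which the grading scale defines without a size, so a small Grade 4 reaction would be left out of the SAP's local-reaction summaries

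*SAP*

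**What the plan says.** SAP 3.1.1.1 states the floor twice. First as a definition: "For redness and swelling, the reported size must be at least 2.5 cm (0.98 inches) to be deemed as a local reaction". Then as an exclusion: "Redness and swelling with a size less than 2.5 cm will not be included in the analysis". Neither sentence refers to grade.

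SAP Table 5, in the same section, grades redness and swelling by diameter for Grades 1 to 3, starting at 2.5 cm. Grade 4 has no diameter. For redness, the criterion in Table 5 and in Protocol Table 9 is "Necrosis or exfoliative dermatitis"; for swelling it is necrosis alone. Footnote b to the table adds: "Induration/swelling should be evaluated and graded using the functional scale as well as the actual measurement".

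Protocol 8.2.3.1 says that redness and swelling are measured and then categorized in the analysis, from absent to potentially life-threatening, using Table 9. It has no separate sentence removing reactions by size. Protocol 8.2.3 also requires: "All reported Grade 4 local and/or systemic reactions must be confirmed by an investigator or a medically qualified person". Protocol 9.4.2 plans that "the number and percentage of subjects reporting at least one local reaction will be summarized by worst grade using the Safety Set".

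SAP 6.1.1.2 summarizes local reactions within 7 days of each dose by maximum severity and cumulatively over severity levels, and has no rule for small Grade 4 reactions.

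**The concern.** The floor and the grading scale agree for Grades 1 to 3 and disagree for Grade 4. A lesion can meet the most severe criterion in the table and still fail the size test stated just above it.

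Local reactions up to 7 days after each dose are a primary safety endpoint in Parts A, B and C (SAP 3.1.1). If the floor is programmed as written, the Grade 4 redness and swelling cells could show zero despite a medically confirmed case, and the subject's maximum severity would be taken from whatever other local reactions were recorded.

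**Working it through.** No arithmetic bears on the point itself, and the plan gives no figure to reproduce. The check is to apply the two rules in SAP 3.1.1.1 to example reactions and see where they part.

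| Example | Grade by SAP Table 5 | Floor in SAP 3.1.1.1 | Agree? |
|---|---|---|---|
| Redness 2.0 cm, no necrosis or exfoliative dermatitis | none | excluded | yes |
| Redness 3.0 cm, no necrosis or exfoliative dermatitis | 1 | included | yes |
| Redness 3.0 cm with necrosis | 4 | included | yes |
| Redness 2.0 cm with necrosis or exfoliative dermatitis | 4 | excluded | **no** |
| Swelling 2.0 cm with necrosis | 4 | excluded | **no** |

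**Does the order of steps settle it?** The floor decides what is a local reaction. Grading then applies to solicited local reactions, and maximum severity is derived for subjects with at least one local reaction. Read in that order, the record is dropped before it is graded. A programmer who graded first and applied the floor only to Grades 1 to 3 would avoid the problem, but the text does not say to do that.

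**Does anything put the event back?** SAP 6.1.1.2 has no exception. Medical confirmation of Grade 4 (Protocol 8.2.3, SAP 3.1.1.3) verifies the event but is not linked to the derivation. SAP Section 8, which lists departures from the protocol's analysis, does not mention the floor.

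**What does the protocol's rule give?** Categorizing by Protocol Table 9 makes the 2.0 cm necrotic lesion Grade 4, and it is counted. The loss comes from the SAP sentences alone.

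**Where else would the event appear?** Under SAP 3.1.1.3, e-diary events "should not be reported as AEs unless the event meets criteria for an SAE or starts after Day 7", or start on Days 1 to 7 and continue past Day 7. For an onset within Days 1 to 7:

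| | Resolved by Day 7 | Continues past Day 7 |
|---|---|---|
| Serious | SAE outputs | SAE and AE outputs |
| Not serious | **no summary table** | AE outputs |

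The SAP 6.1.1.1 overview has a row for the persistent cases ("Any solicited AE that starts on Days 1 to 7 and continues longer than 7 d post-vaccination") as well as SAE rows.

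**Illustration of one omitted event.** The documents give no rate, so this is not an estimate of effect. Assume exactly one such event and the planned cohort size as denominator; the real denominator is the Reactogenicity Set, which may be smaller. SAP 6.1.1.2 names the 95% Clopper-Pearson interval. For 0 of n the upper limit is 1 − 0.025^(1/n). For 1 of n the lower limit is 1 − 0.975^(1/n), and the upper limit is the 97.5% quantile of Beta(2, n − 1).

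| Cohort | n | Grade 4 reported with the floor: 0/n | Grade 4 counted: 1/n |
|---|---|---|---|
| Part A, each | 20 | 0% (0 to 16.8%) | 5.0% (0.1 to 24.9%) |
| Part C, Cohort 7 or 8 | 90 | 0% (0 to 4.0%) | 1.1% (0.03 to 6.0%) |
| Part B, each | 375 | 0% (0 to 0.98%) | 0.27% (0.007 to 1.48%) |

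**The case against.** The strongest reply is that the omitted case is close to empty. It has to be necrosis or exfoliative dermatitis, under 2.5 cm, not serious, and gone by Day 7. Protocol 10.3.1.4 says that important medical events needing treatment to prevent a worse outcome should usually be considered serious, the table labels Grade 4 as potentially life-threatening, and each such report is medically confirmed. Most real cases would therefore reach the SAE or AE tables, and the Safety Review Committee reviews all safety data about every 4 weeks (Protocol 10.1.5).

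A second reply is that the floor has an evident purpose. It restates the lower bound of Grade 1, and a sensible reader of Table 5 would still grade necrosis as 4. A third is that the e-diary and case report form specifications are not in the documents, so it cannot be shown that a necrosis record would pass through the size filter at all.

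Much of this stands. It makes the point minor and rules out any claim that events were in fact lost. It does not remove the conflict. Seriousness is not automatic, because Protocol 10.3.1.6 has severity and seriousness assessed independently. The AE routes do not return an event to the local-reaction tables. And a rule that excludes by size without exception should not depend on the programmer choosing to read past it.

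**Conclusion.** The point holds as an inconsistency in the SAP, of minor importance. Followed literally, SAP 3.1.1.1 leaves a confirmed Grade 4 redness or swelling under 2.5 cm out of the SAP's local-reaction counts and maximum-severity summaries. The consequence is descriptive, and no hypothesis test, sample size or decision rule is affected. The conclusion assumes that the floor is programmed as written and that a Grade 4 record carries a diameter below 2.5 cm.

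Three stronger readings are tempting, and the documents do not support them:

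- That severe local reactions would vanish from safety reporting. Serious or persistent cases are still recorded and tabulated as AEs or SAEs. Only a non-serious case resolved by Day 7 is absent from every table.
- That the worst-grade and Grade 3 or higher summaries in Protocol 9.4.2 are themselves at fault. The protocol has no exclusion by size, and its own rule would count the event.
- That footnote b shows functionally graded swelling being lost at Grades 1 to 3 as well. Table 5 prints no functional criteria for swelling at those grades, so the conflict is confined to Grade 4.

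**What to change.** Limit the 2.5 cm floor in SAP 3.1.1.1 to the size-based Grades 1 to 3, and add: *Any redness or swelling meeting the Grade 4 criterion in Table 5 is counted as a local reaction whatever its diameter.* Use the medical confirmation of Grade 4 that both documents already call for to identify these events.

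The cost is one sentence and a small change to the derivation. Nothing changes in trial conduct, which SAP 8.3 says ended on 04 October 2023. One thing needs checking: the documents do not describe the data field that holds the Grade 4 confirmation, so the sponsor should verify that necrosis or exfoliative dermatitis can be identified separately from the diameter. If the SAP is not reopened, the sponsor can check whether any confirmed Grade 4 redness or swelling under 2.5 cm exists and state in the clinical study report which rule was applied.
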